The Effect of Routine Activity on the Risk for Preterm Delivery in Women with a Short Cervix: A Randomized Controlled Trial

Principal Investigator: [name] [name]

Email: [contact]

[contact]

Co-Investigator: [name]

Institution: Department of Obstetrics and Gynecology, Edith Wolfson Medical Center

[name]

Study Protocol: 124-24-WOMC

Version: 2.0

Date: 18.12.2024

Background:

Preterm birth is defined as delivery occurring before the completion of 37 weeks of gestation (1). The incidence of preterm birth is estimated to be approximately 10% of all deliveries (2) and represents a significant cause of perinatal morbidity and mortality (3-6). Pregnant women with a shortened cervix, as determined by transvaginal ultrasound, are at an increased risk of preterm delivery (7-8). Traditionally, bed rest has been recommended for women at risk of preterm birth. Studies suggest that approximately 18% of pregnancies in the United States receive a recommendation for bed rest at some point during pregnancy (9). The rationale for bed rest has been based on the assumption that physical exertion and strenuous activity could be associated with preterm labor and that rest may reduce uterine activity (9-11). Despite the widespread use of this recommendation in obstetrics, very few prospective randomized trials have been conducted to examine its effectiveness. A recent Cochrane review on bed rest for preventing preterm birth identified only one study, which included 1,266 women (12). The study found no significant difference in preterm birth rates before 37 weeks between women assigned to full bed rest and those who did not receive any specific intervention (7.9% vs. 8.5%). Additionally, there was no evidence that bed rest reduced preterm birth rates among women with a short cervix (13). Only one study has quantitatively assessed the relationship between physical activity and preterm birth risk in women with a short cervix (14). The study evaluated 49 women with a short cervix who were instructed to wear a step-counting device for at least one week. Participants were not given specific instructions on activity limitations. The study found no benefit to reducing physical activity levels for preventing preterm birth. In fact, women with lower step counts had a higher rate of preterm birth.

Rationale for the Study: The study aims to examine the effect of routine activity in pregnant women with a short cervix on gestational age at delivery.

Study Objective: To assess the impact of routine activity on the risk of preterm birth in pregnant women between 24 and 34 weeks of gestation with a sonographically diagnosed short cervix.

Primary Outcome:

- Gestational age at delivery.

Secondary Outcomes:

- Incidence of preterm contractions.
- Incidence of premature rupture of membranes (PPROM).
- Mode of delivery (cesarean section, instrumental delivery, spontaneous vaginal delivery).

Methods

Study Design This is a prospective, randomized, controlled trial comparing two groups.

Study Procedure

1. A computer-generated 1:1 randomization scheme will allocate participants to either the intervention or control group.
2. Women attending hospitalization or high-risk pregnancy clinics at Wolfson Medical Center between 24+0 and 34+6 weeks of gestation, diagnosed with a short cervix (<25 mm) via transvaginal ultrasound, will be approached by a physician and informed about the study.
3. Upon obtaining informed consent, participants will be enrolled in the study. Upon discharge, they will receive a smart band to monitor step counts. The monitoring period will last for two weeks.
4. Participant allocation will be conducted using the pre-generated randomization scheme and sealed opaque envelopes managed by an external research nurse.
5. All participants, regardless of study group assignment, will be granted medical leave from work.
6. **Control Group (Routine Activity):** Participants in this group will be instructed to continue their normal, non-strenuous routine activities without a recommendation for maximal rest.
7. **Intervention Group (Maximal Rest):** Participants in this group will be instructed to follow maximal rest guidelines, avoiding strenuous activities such as prolonged standing, carrying heavy items, or lifting children.
8. Participants will continue to receive regular follow-up in hospitalization or high-risk pregnancy clinics as per standard departmental protocols.
9. Each participant's smart band data will be linked to a dedicated email address, ensuring step count data remains blinded to researchers until study completion.
10. Step-count monitoring will cease immediately after delivery.

Eligibility Criteria

Inclusion Criteria:

- Pregnant women between 24+0 and 34+6 weeks of gestation.
- Singleton pregnancies.
- Short cervix (<25 mm) confirmed via transvaginal ultrasound.
- No medical contraindication to mobility.

Exclusion Criteria:

- Declining study participation.
- Medical recommendation to restrict mobility (e.g., symphysiolysis, high fall risk).
- Significant maternal comorbidities.
- Fetal distress.
- Vaginal bleeding.
- PPROM.
- Medical indication for immediate preterm delivery.
- Twin or higher-order multiple pregnancies.

Withdrawal Criteria:

- Medical indication requiring preterm delivery or urgent intervention (e.g., fetal distress, maternal complications).
- Medical condition requiring strict activity limitation, contrary to group allocation.
- Participant non-compliance with study protocol, including smart band usage.

Study Variables

Primary and secondary endpoints will be assessed based on: Step count. Number of follow-up days. Gestational age at delivery. Obstetric outcomes. Demographic characteristics (BMI, age, parity, history of preterm birth). Cervical length at diagnosis.

Data Collection

Medical data, including height, weight, age, and delivery details, will be collected from the hospital's electronic medical system (Cameleon).

Step count data will be retrieved from the dedicated email address linked to each participant's smart band at the end of the monitoring period.

Statistical Methods

Sample Size: 100 participants.

Data Analysis: Data will be analyzed using SPSS. Continuous variables will be presented as median and interquartile range (IQR). Comparisons will be made using t-tests or Mann-Whitney tests for continuous variables. Categorical variables will be compared using chi-square or Fisher's exact tests. Correlations will be

analyzed using Pearson or Spearman tests. Logistic regression will be conducted to identify factors significantly associated with preterm birth.

Study Timeline Duration: Two years.

Participant follow-up: Begins at enrollment and continues until delivery.

Step count monitoring: Two-week period during pregnancy.

Ethical Considerations

The study is funded by the Department of Obstetrics and Gynecology, Edith Wolfson Medical Center.

Participants may withdraw at any time without affecting their medical care.

The study question is specific to pregnant women, and the results may help optimize management strategies for this population.

Data Privacy

Each participant will be assigned a random identification number. Personal identifiers (name, ID number, address) will be securely stored on the principal investigator's locked computer, accessible only to authorized personnel.

Informed Consent

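### Does ending the step record at delivery build a link between fewer steps and preterm birth into the analysis?

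*Protocol*

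**What the plan says.** Study Procedure, item 3, starts the recording: "Upon discharge, they will receive a smart band to monitor step counts", and adds "The monitoring period will last for two weeks". Item 10 ends it early where necessary: "Step-count monitoring will cease immediately after delivery".

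The Study Timeline gives two different spans: "Participant follow-up: Begins at enrollment and continues until delivery" and "Step count monitoring: Two-week period during pregnancy".

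Study Variables opens its list with "Primary and secondary endpoints will be assessed based on: Step count. Number of follow-up days. Gestational age at delivery" and goes on to obstetric outcomes, demographic characteristics and cervical length.

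Under Statistical Methods, Data Analysis, correlations are to be "analyzed using Pearson or Spearman tests. Logistic regression will be conducted to identify factors significantly associated with preterm birth". No pair of variables is named for the correlations and no covariates for the regression. The protocol does not say whether step count is a total or a daily mean.

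**The concern.** The primary outcome is gestational age at delivery, and delivery also ends the step record. If steps were summed over whatever record exists, an early delivery would lower the sum by itself, so fewer steps would appear to go with earlier delivery even under no effect. The Background cites a pilot study of 49 women in which lower step counts went with more preterm birth. An artefact in the same direction could be taken for confirmation.

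The second worry is the follow-up-days variable. Read by the Timeline's definition of follow-up, it runs from enrolment to delivery and is the outcome minus gestational age at entry. Entered as a predictor of preterm birth, it would be significant by construction.

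**Working it through.** The plan gives no figure of its own on this point, so there is none to reproduce.

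**Inputs from the protocol.** Entry from 24+0 to 34+6 weeks; preterm means before 37 completed weeks; 14 days of monitoring; 100 women.

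**Assumed inputs.** The share delivering within 14 days, the distribution of daily steps, and any fall in activity before delivery. The protocol gives none of these.

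**1. Who can have a shortened record.** Latest entry: 34 × 7 + 6 = 244 days. Adding 14 gives 258 days, or 36+6. The preterm threshold is 37 × 7 = 259 days. If the band is worn from enrolment, every record cut short by delivery therefore belongs to a preterm birth. If a woman entered at 34+6 is discharged k ≥ 1 days later, her window ends at 258 + k ≥ 259, so a few term births could also be cut short.

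**2. Effect on a total.** Total steps = daily rate × min(14, days from band to delivery). At a constant rate, delivery on day 7 gives 7/14 = 50% of a full total.

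**3. Size under no effect.** Simulation A: 1,500 trials per row, entry uniform over 24+0 to 34+6, daily steps log-normal (median 5,000, log-SD 0.4) and independent of outcome, 20% of the remaining women preterm later, monitoring from entry. Test: Mann-Whitney, preterm against term, two-sided 5%.

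| Delivered within 14 days (assumed) | Total steps, false positives | Steps per day, false positives |
|---|---|---|
| 2% | 8% | 5.3% |
| 5% | 18% | 4.9% |
| 10% | 41% | 5.5% |
| 15% | 64% | 4.9% |
| 20% | 83% | 5.3% |

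The last column is expected: with a constant daily rate, dividing by monitored days recovers the rate exactly.

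**4. If activity falls before delivery.** Simulation B: 1,000 trials per setting, four assumed settings with 3.9%, 5.0%, 7.3% and 8.3% delivering within 14 days, and 25% fewer steps in the rest arm. Spearman false positives for steps per day, in that order:

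- no fall: 4.7%, 5.7%, 4.2%, 4.1%
- 35% fall: 6.6%, 6.1%, 8.3%, 7.3%
- 70% fall in the last 3 days: 7.2%, 10.8%, 14.0%, 12.4%

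The simulation error at 5% is √(0.05 × 0.95 / 1,000) = 0.7 percentage points, so the no-fall figures cannot be told from 5%.

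**5. Follow-up days.** Read as days to delivery, it equals gestational age at delivery minus gestational age at entry. A birth is preterm exactly when entry plus this number is below 259. Alone, it separates preterm from term with an AUC of 0.83 to 0.89 in simulation B and 0.89 to 0.94 in simulation A. Read as monitored days, it is the divisor in step 3.

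**6. Price of a day-14 landmark.** Analysing only women undelivered at day 14 holds false positives at 3% to 6% throughout simulation B. The preterm births lost are 3.9/17.2 = 23%, 5.0/21.6 = 23%, 7.3/21.1 = 35% and 8.3/33.7 = 25%. The standard error of the step log odds ratio rises by 10% to 21%.

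**The case for a change.** The case for changing the plan is that the stopping rule, the variable list and the definition of follow-up are all on the page, and that the direction of bias follows from the dates alone. Step count is the only activity measure listed, and it is named as a basis for assessing endpoints. The literal Timeline reading of follow-up gives the circular version. Clarifying costs a sentence, and step data stay blinded to the researchers until study completion (Study Procedure, item 9), so the metric could still be fixed without sight of them.

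Much of this stands. Total steps would be biased if used, and the follow-up-days label has two readings. The withdrawal criterion "Medical indication requiring preterm delivery or urgent intervention" does not remove the problem, because spontaneous early deliveries remain. With half of the early deliveries withdrawn (an assumed share), simulation B still gives 7% to 9% for total steps by Spearman and 6% to 11% by logistic regression.

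What does not stand is the step from a possible misuse to an error in the plan. Appearing in Study Variables does not make an item a predictor: the same list contains gestational age at delivery itself and the obstetric outcomes. Item 10 is not at fault either, since stopping the band at delivery is the only sensible rule and any remedy would keep it. Nor is information lost: the step count, the date of discharge and the date of delivery give the daily mean.

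**Conclusion.** No change to the plan follows. This is a gap that an analyst fills sensibly. With unequal recording times, mean steps per monitored day is the ordinary choice, and the protocol lists both the count and a number of days. Days to delivery would not normally be offered as a predictor of preterm birth. Step metric and covariates are details a protocol commonly leaves to the SAP.

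The bias in total steps is real but conditional: from 8% false positives at 2% early delivery to 41% at 10%, with both shares assumed. The daily mean removes it if activity is steady up to delivery. What remains depends on an assumed fall in activity: 6% to 8% at a 35% fall and 7% to 14% at a 70% fall, for the Spearman test. Guarding against that with a day-14 landmark would give up about a quarter to a third of the preterm births in a trial of 100 women and restrict the result to women undelivered at that point. That is a fair trade-off either way. It suits an optional sensitivity analysis, not a requirement.

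The step correlations and the risk-factor regression are exploratory. The comparison of gestational age at delivery between the allocated arms does not use the step record and is untouched by this point.

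### The Withdrawal Criteria do not say what a woman is withdrawn from, and one criterion includes an event that is itself a low value of the primary outcome

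*Protocol*

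**What the plan says.** The Withdrawal Criteria section of the Protocol gives three reasons:

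1. "Medical indication requiring preterm delivery or urgent intervention (e.g., fetal distress, maternal complications"
2. "Medical condition requiring strict activity limitation, contrary to group allocation"
3. "Participant non-compliance with study protocol, including smart band usage"

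The list is separate from the entry rules. The Exclusion Criteria already bar "Medical indication for immediate preterm delivery" and "Medical recommendation to restrict mobility (e.g., symphysiolysis, high fall risk", and the Inclusion Criteria require "No medical contraindication to mobility". The withdrawal list therefore applies to women who have already been enrolled.

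The Primary Outcome is "Gestational age at delivery", with no restriction to spontaneous birth. On the band, Study Procedure item 3 says "The monitoring period will last for two weeks". The Study Timeline has follow-up run from enrolment to delivery and names no exception. Data Collection takes delivery details from the hospital's electronic record.

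No passage says which of four things withdrawal ends: the allocated advice, band monitoring, outcome follow-up, or inclusion in the primary comparison.

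**The concern.** In ordinary use, a withdrawn participant has left the study. On that reading each criterion causes a different problem.

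- **Criterion 1.** A medically indicated preterm delivery is a low value of the primary outcome. Removing it selects on the outcome and erases any true difference between arms in how often or how early such deliveries occur. The urgent-intervention part of the criterion need not be a low value.
- **Criterion 2.** Study Procedure items 6 and 7 assign routine activity to one arm and maximal rest to the other. A need for strict limitation conflicts with the first and not, in practice, with the second, so removals would come from one arm.
- **Criterion 3.** Band wear has no bearing on whether gestational age at delivery can be observed, yet it could decide whether a woman counts.

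At stake is whether the primary comparison is between the groups as randomised. If withdrawal ends only the advice or the band, nothing is lost.

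**Working it through.** **Which reading the text supports.** The follow-up line in the Study Timeline favours keeping withdrawn women, but does not mention them. Two other provisions point the other way.

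- Item 10 of the Study Procedure already stops step counting at delivery. If withdrawal ended only the band or the advice, the preterm-delivery part of criterion 1 would have almost no function.
- Item 9 keeps step counts blinded until study completion, while Data Collection has them retrieved when monitoring ends. On either timing, non-wear judged from those data would be known only after the band period, when no band monitoring is left to end.

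**Timing.** A woman enrolled at 24+0 who delivers at 37+0 is followed for 37 - 24 = 13 weeks. The band covers two of them.

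**Inputs for the sizing.** From the Protocol: 100 women allocated 1:1, so 50 per arm. The Protocol gives no SD, withdrawal share or gap in gestational age, so these are assumed: SD 2.5-3 weeks, shares of 2-10%, gaps of 0-4 weeks.

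**Scale.** SE of the difference = SD × √(2/50) = 0.2 × SD, or 0.50-0.60 week. The difference detectable with 80% power (two-sided 5%) is about 2.80 × SE, or 1.40-1.68 weeks.

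**Criterion 2, removal from the routine arm only, no true effect.** Let p be the share removed and g the number of weeks by which those women deliver earlier than the rest. The full arm's mean is the kept women's mean minus p × g, so removal shifts the arm by p × g. The table shows rejection rates from 50,000 simulated trials per setting (pooled t-test, two-sided 5%, simulation error about 0.1 percentage point). Each cell gives SD 2.5 / SD 3.

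| Removed | Bias for g = 1 to 4 (weeks) | g = 0 | g = 1 | g = 2 | g = 3 | g = 4 |
|---|---|---|---|---|---|---|
| 2% | 0.02-0.08 | 4.9 / 4.8% | 5.1 / 5.0% | 5.0 / 5.1% | 5.1 / 5.2% | 5.3 / 5.2% |
| 5% | 0.05-0.20 | 4.9 / 5.2% | 5.1 / 4.9% | 5.2 / 5.3% | 5.9 / 5.7% | 6.5 / 6.2% |
| 10% | 0.10-0.40 | 5.0 / 5.1% | 5.5 / 5.0% | 6.5 / 6.2% | 8.4 / 7.3% | 10.9 / 9.1% |

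With every woman kept as allocated, the rate is 4.8-5.2% throughout. The bias favours routine activity if the removed women deliver earlier, and rest if they deliver later.

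**Criterion 1, removal in both arms.** Suppose the arms differ only in their indicated deliveries, with shares p₁ and p₂ delivering g₁ and g₂ weeks early. The true difference, p₂ × g₂ - p₁ × g₁, becomes zero on removal.

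| Shares | Weeks early | True difference (weeks) | After removal |
|---|---|---|---|
| 10% v 10% | 3 v 3 | 0.10×3 - 0.10×3 = 0.00 | 0.00 |
| 5% v 5% | 2 v 4 | 0.05×4 - 0.05×2 = 0.10 | 0.00 |
| 10% v 10% | 2 v 4 | 0.10×4 - 0.10×2 = 0.20 | 0.00 |
| 5% v 10% | 2 v 2 | 0.10×2 - 0.05×2 = 0.10 | 0.00 |
| 5% v 10% | 4 v 4 | 0.10×4 - 0.05×4 = 0.20 | 0.00 |

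**Criterion 3.** The Protocol gives no basis for a share, a gap or a direction, so no figure is offered.

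**The case against.** The strongest reply is that analysis populations usually belong in the SAP, which was not available, and that the Protocol never says withdrawn women are dropped from the comparison. This has force for the analysis set. It does not settle the point, because the withdrawal rule stands in the Protocol itself. Whether delivery data are still collected after withdrawal is a matter of conduct, and an SAP cannot recover outcomes that were not collected.

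Second, for an indicated preterm delivery the outcome would normally be on record, since delivery completes follow-up. That is right. The risk under that part of criterion 1 is exclusion from the comparison, not a missing value.

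Third, the Protocol lists enrolment before allocation in the Study Procedure, so a woman could meet criterion 1 before she is allocated, and removing her then would cause no imbalance. This is possible for some women but not for those already following their allocated advice.

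Fourth, the one-sided reading of criterion 2 is an inference, because item 7 describes maximal rest only by examples. It is the more natural reading, but the simulation depends on it.

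Finally, the effect is small under modest assumptions. Women with mobility restrictions are screened out at entry, so the share may be low, and the Protocol's examples (symphysiolysis, fall risk) do not establish a gap. This stands and limits how serious the point is.

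**Conclusion.** The concern holds in conditional form. The Protocol sets withdrawal rules tied to the outcome, to the allocated arm and to adherence, and leaves open whether they remove women from follow-up or from the primary comparison. If they do, criterion 2 is close to harmless at 2% removed and raises type I error to at most 6.5% at 5% removed and 10.9% at 10% removed. Those maxima need a four-week gap, an SD of 2.5 weeks and removal from one arm only. Under criterion 1, true differences of 0.1-0.2 week would be erased in the unequal settings examined, which is small beside an SE of 0.50-0.60 week. There is no bias when shares and gaps are equal across arms, or when removed and kept women do not differ. This is a cheap improvement in wording. Confidence is medium, because the sizes rest wholly on assumed inputs and the follow-up line leans towards the harmless reading.

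**What to change.** Add to the Withdrawal Criteria section that:

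- meeting a criterion ends at most the allocated activity advice or the band monitoring, and does not end outcome follow-up;
- gestational age at delivery is collected for every randomised woman who has not withdrawn consent;
- the primary comparison keeps each woman in her allocated arm, whatever the indication for delivery, any later activity restriction, or band wear;
- any compliance-based analysis is labelled as a sensitivity analysis.

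The cost is a few sentences. Keeping non-adherent women dilutes the contrast somewhat, which the sensitivity analysis can show. A withdrawn woman who delivers at another hospital will need some tracing, as any participant would. No change to clinical management is proposed.

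### Step counts are collected without any wear information, so partial-day non-wear (and whole-day non-wear, if only totals are kept) cannot be separated from low activity

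*Protocol*

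**What the plan says.** Study Procedure, item 3, gives the band one purpose: "Upon discharge, they will receive a smart band to monitor step counts". It adds: "The monitoring period will last for two weeks". Data Collection then says: "Step count data will be retrieved from the dedicated email address linked to each participant's smart band at the end of the monitoring period". Study Variables reads: "Primary and secondary endpoints will be assessed based on: Step count. Number of follow-up days. Gestational age at delivery", followed by obstetric outcomes, demographic characteristics and cervical length. No section mentions wear time, worn days, a minimum wear rule or a wear diary.

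Three other provisions bear on the point:

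- Study Procedure, item 7, on the rest arm: "Participants in this group will be instructed to follow maximal rest guidelines, avoiding strenuous activities", with prolonged standing, heavy carrying and lifting children as examples.
- Withdrawal Criteria include: "Participant non-compliance with study protocol, including smart band usage". No threshold or means of detection is given.
- Study Procedure, item 9, links the band data to a dedicated account, "ensuring step count data remains blinded to researchers until study completion".

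**The concern.** A step count is low when a woman moves little, and also when she moves normally but leaves the band off. One arm is asked to move less, so the expected sign of adherence in that arm points the same way as non-wear.

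Steps are the only listed objective evidence that the two instructions produced different activity. That evidence matters here because every participant gets medical leave and the control arm is also told to keep to non-strenuous activity, so the true separation may be modest. If gestational age turns out similar in both arms, the reader will need to know whether rest made no difference or whether the arms behaved alike.

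The protocol also plans correlations and a logistic regression for preterm birth, in which steps are a natural candidate. If women with more symptoms wore the band less, low recorded steps would go with early delivery for that reason alone. The Background cites a study in which lower step counts went with more preterm birth, so the same pattern in this trial would readily be taken as confirmation.

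The gap lies in what is collected. A statistical analysis plan can define a valid day, but it cannot recover wear information that was never captured.

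**Working it through.** There is no plan figure to reproduce, because the protocol states no step level, standard deviation or wear rate.

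**Inputs from the protocol:** 14 days of monitoring; 100 participants allocated 1:1, so 50 per arm if even.

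**Assumed inputs, for illustration only:** step levels, standard deviations and wear fractions.

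**Does the number of follow-up days stand in for wear?** No. Study Timeline runs follow-up from enrollment to delivery, so it is a different interval from the two weeks of band use. Even if it meant monitored days, a monitored day need not be a worn day.

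**Model:** recorded steps = true steps × fraction of activity captured while the band is worn.

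1. *Whole-day non-wear, equal true activity of 4,000 steps/day.* Worn 13 of 14 days: 4,000 × 13/14 = 3,714. Worn 11 of 14 days: 4,000 × 11/14 = 3,143. The spurious deficit is 1 − 11/13 = 15.4%. Dividing by worn days restores equality: (4,000 × 13)/13 = (4,000 × 11)/11 = 4,000.

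2. *Partial capture, equal true activity of 4,000.* Capture of 70% (rest) v 90% (routine) records 2,800 v 3,600, a false gap of 800. With an SD of 2,000 for recorded steps, the standard error is 2,000 × √(2/50) = 400. The chance of two-sided significance at 0.05 in that direction is Φ(800/400 − 1.96) = Φ(0.04) ≈ 52%. Capture of 60% v 90% gives a gap of 1,200 and Φ(3 − 1.96) ≈ 85%.

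3. *A real difference, 3,000 (rest) v 4,000 (routine).* Capture of 100% v 75% records 3,000 v 3,000, so the difference vanishes. Capture of 95% v 75% records 2,850 v 3,000, leaving 150 of the true 1,000. Capture of 75% v 95% records 2,250 v 3,800, inflating it to 1,550.

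4. *Equal capture in both arms.* 80% v 80% with equal activity records 3,200 v 3,200: no bias. With a true 3,000 v 4,000, 90% capture in both records 2,700 v 3,600: the difference shrinks from 1,000 to 900.

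5. *Noise from wear unrelated to activity.* For true steps X (mean 4,500, SD 1,500) and an independent wear fraction W, the correlation of true with recorded steps is E(W) × SD(X) / SD(XW).
   - W uniform on 0.6–1.0: E(W) = 0.8, E(W²) = 0.6533. Var(XW) = 22.5 million × 0.6533 − 3,600² = 1.74 million, SD 1,319. Correlation = 0.8 × 1,500/1,319 = 0.91.
   - W uniform on 0.4–1.0: E(W) = 0.7, E(W²) = 0.52. Var(XW) = 22.5 million × 0.52 − 3,150² = 1.78 million, SD 1,333. Correlation = 0.7 × 1,500/1,333 = 0.79.

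**The case against.** The strongest reply is that rest in this protocol is not immobility. Item 7 describes avoiding strenuous activity, so a woman in the rest arm would still walk about at home. A reader might infer that an unworn band always looks like rest. The documents do not support that: if counts are kept by day, a zero-step day would point to non-wear. This stands, and it limits the point to partial-day non-wear and to whole-day non-wear when only totals are kept. It also means the 13 v 11 day example is the case that daily counts could reveal. The protocol states neither daily resolution nor a rule for zero-step days.

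A reader might also infer that resting women would be withdrawn as non-wearers. Item 9 keeps step data from the researchers until study completion, so low counts should not drive withdrawals during the trial. How band use is to be checked is left unsaid, but that is a separate matter about the withdrawal criterion.

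Other replies have partial force. The protocol does not say that wear information is excluded, and the device is unnamed, so some wear data might be recoverable. That is a reason to state it, since nothing in the text secures it. Nothing in the documents suggests that wear will differ by arm or by symptoms. Detailed valid-day rules may properly sit in the statistical analysis plan, whereas capturing wear cannot be left until then.

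**Conclusion.** The point holds in limited form. Step counts are retrieved, no wear information is named, and no listed variable substitutes for it. Bias in the step comparison between arms requires wear to differ by arm; equal non-wear mainly shrinks a true difference and adds noise. Distortion of step–outcome correlations in a particular direction requires wear to be related to symptoms or outcome. Every size shown, including the 15%, rests on assumed step levels and wear and is not a forecast for this trial.

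A reader might infer that the main result is compromised. It is not directly affected: steps are neither the primary nor a listed secondary outcome, and wear error does not enter the randomized comparison of gestational age at delivery. What is weakened is the evidence that the arms differed in activity, and any analysis relating steps to outcome. The change is worth making because it is small, and because wear information that was not captured cannot be restored once monitoring ends.

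**What to change.** In Data Collection, state that daily step counts will be retrieved together with daily wear time, or with a 14-day worn/not-worn log if the device does not record wear. Wear time is preferable, because a simple daily log identifies unworn days but not partly worn ones.

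Base the step analyses on mean steps per worn day, with the threshold for a valid day fixed before step data are unblinded, in the protocol or the statistical analysis plan. Report worn days by arm. Assess band use from the wear information and not from step counts, which stay blinded under Study Procedure, item 9; the wear information should therefore be available separately from the counts.

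The cost is a little more data collection: an added export field if the device records wear, otherwise a log for participants to fill in. A few women will have too few worn days for the step analyses. They should stay in the primary analysis.
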